1. OBJECTIVES

Primary Objective

The primary objective of the study is to determine the Overall Response Rate (ORR) (complete remission [CR] + partial remission [PR]) in patients with relapsed or refractory (R/R) FL.

Secondary Objectives

Determine the genetic and other novel biological markers that are predictive of response and resistance to TGR-1202 in patients with relapsed or refractory FL.

Describe the Progression Free Survival (PFS), Duration of Response (DoR) after treatment with TGR-1202

Describe the number of dose delays and dose reductions

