- Study drug will be made available to responding patients for a total of three years from initiation of therapy. If TGR-1202 becomes commercially available during the active period on study, an attempt will be made to obtain this agent through commercial insurance. If coverage is not available, it will be provided for a period of three years as stated above.

Duration of Follow Up

Patients will have an end-of-study visit 4 weeks \pm 1 week after the last dose of the study drug to evaluate safety. Patients will be further followed every three months for one year, or until they begin a new treatment for their disease, for evaluation of delayed toxicity. Patients removed from study for unacceptable AE will be followed until resolution or stabilization of the AE. Further follow-up should be performed according to standard clinical practice.

For patients who achieve stable disease or better after 6 cycles of therapy, tumor assessment will be performed by medical history, physical exam, complete blood count with differential and blood chemistries every 3 months, and CT (PET/CT optional but encouraged) at least every 6 months, until progression of disease occurs.

Criteria for Removal from Study

Patients will be removed from treatment when any of the criteria listed in Section 5.3 applies. The reason for and date of patient removal must be documented in the CRF.

Subjects/patients may withdraw consent at any time or be dropped from the study at the discretion of the investigator should any untoward effects occur. In addition, a subject/patient may be withdrawn by the investigator if he/she violates the study plan, or due to administrative and/or safety reasons. The investigator or study coordinator will notify the appropriate parties within 2 business days of becoming aware of an adverse event causing withdrawal of the subject from the study (Section 7). When a subject discontinues/withdraws prior to study completion, all applicable activities scheduled for the final study visit should be performed at the time of discontinuation. Any adverse events present at the time of discontinuation/withdrawal will be followed until resolution.

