6. DOSING DELAYS/DOSE MODIFICATIONS

- For a new treatment cycle to begin, patients must meet the criteria outlined in section 5. Moreover, all other toxicity must have returned to grade ≤ 2 . If either of these conditions are not met, the study drug will be held.
- If interruption of study drug lasts for more than 28 days, treatment should be discontinued and the subject should be removed from the study (please contact the study chair to discuss longer interruptions).
- Patients who experience toxicity and require the study drug to be withheld may not be candidates for biopsy. Patients who miss 4 or more doses of drug prior to a planned biopsy should be considered ineligible for biopsy. The treating physician will make the ultimate decision in this regard.

Dose Modifications

Patients will be monitored continuously for toxicity while on study therapy. Toxicity will be assessed using the NCI CTCAE v4.0 (<http://evs.nci.nih.gov/ftp1/CTCAE/CTCAE>) grading scale. If a patient has an adverse event of particular severity or had an adverse event at least possibly related to study drug, then dose modifications will be made according to the guidelines.

Deviations from these guidelines may occur only if agreed upon by the Principal Investigator. There should be no attempt to make up for doses omitted due to toxicity.

A maximum four (4) week delay of treatment for recovery from toxicity is allowed to recover from hematologic toxicities to \leq Grade 3 or non-hematologic toxicities to \leq Grade 2 or to baseline level. If greater than a four (4) week delay is necessary, then the patient should discontinue treatment

and continue to be followed for progression. If a patient withdraws consent or has documented progression, an end of study visit should be completed.

Recommended treatment interruptions/holds or dose modifications are summarized below and may be based on the clinical judgment of the Investigator with notification to the Principal Investigator. For an individual patient, dose reductions and discontinuations may be more conservative than indicated. (i.e., to dose-reduce or discontinue for non-hematologic toxicity of lower grades) based on the clinical judgment of the Investigator with notification to the Medical Monitor/Sponsor.

Summary of Dose Holds for Treatment-Related Toxicities

NCI-CTCAE Grade	Dose Delay and/or Modification
Hematologic Adverse Event	
Neutropenia	
Grade ≤ 2 neutropenia	Maintain current dose. Consider supportive care as warranted.

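### Follow-up for progression after an early stop without progression is not expressly required for several stopping reasons and is inconsistent across Sections 5, 6, 10 and 11, so PFS and DoR may be biased in a direction the documents do not fix

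*Combined protocol and SAP*

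**What the plan says.** The secondary objectives in Section 1 include this one: "Describe the Progression Free Survival (PFS), Duration of Response (DoR) after treatment with TGR-1202". Section 13 gives no event definition, censoring rule or estimator for either endpoint.

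Four places bear on how progression is observed once study drug stops.

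- **Section 5, Duration of Follow Up.** After the four-week safety visit, quarterly visits run for a year, with this alternative end point and this purpose: "or until they begin a new treatment for their disease, for evaluation of delayed toxicity". Beyond that, "Further follow-up should be performed according to standard clinical practice". The next paragraph contains the explicit rule on tumour assessment up to progression: "For patients who achieve stable disease or better after 6 cycles of therapy, tumor assessment will be performed", with CT at least every 6 months.
- **Section 6, Dose Modifications.** The trigger is a long toxicity delay: "If greater than a four (4) week delay is necessary, then the patient should discontinue treatment". The same sentence then says what happens to that patient afterwards: "and continue to be followed for progression". There is no six-cycle condition here.
- **Section 6, opening bullets.** For an interruption of more than 28 days, "treatment should be discontinued and the subject should be removed from the study".
- **Section 10 (calendar footnote f) and Section 11.** Imaging is at the end of cycles 2 and 6, then every 4 months, or every 6 months once CR is reached. No stable-disease condition is attached. Neither place says whether the schedule continues after early discontinuation.

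**The concern.** Section 5 allows treatment to stop without progression for an unacceptable adverse event, a change in condition or physician judgement. Take a patient who responds at the cycle 2 scan and stops in cycle 4 for an adverse event that involved no delay over four weeks. No sentence expressly requires anyone to find out when that response ends. The three-monthly visits have a toxicity purpose, and they stop after a year or at the next treatment.

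Patients who stop early may well differ in prognosis from those who continue. If their observation ends at the last scan, censoring may be informative, and both PFS and DoR would then describe a selected group. With 20 patients, a handful of such cases can move the curve. Progression dates that were never collected cannot be recovered by analysis, so this has to be settled in the protocol.

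**Working it through.** **1. Coverage by reason for an early stop (before six cycles are completed, no progression)**

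| Reason for stopping | Section 5 | Section 6 | Sections 10 and 11 |
|---|---|---|---|
| Toxicity delay over 4 weeks | Toxicity visits for one year | Followed for progression, and also removed from the study | CT schedule, silent on early stoppers |
| Adverse event without such a delay | Toxicity visits for one year | Nothing on progression | Same |
| Physician judgement or changed condition | Toxicity visits for one year | Nothing on progression | Same |
| Completed 6 cycles with SD or better (for comparison) | Assessed until progression | – | CT schedule |

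Row 1 is contradictory. Rows 2 and 3 are the gap. The scan interval differs as well: at least every 6 months in Section 5, against every 4 months (6 if CR) in Sections 10 and 11.

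**2. The plan's own figure**

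The only design figure is for ORR: 20 patients, 0.33 against 0.60, one-sided 0.10, power 87%. With exact binomial probabilities, the smallest cut-off that keeps the type I error at or below 0.10 is 10 responses:

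- P(X ≥ 10 | n = 20, p = 0.33) = 0.087
- P(X ≥ 10 | n = 20, p = 0.60) = 0.872

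The stated 87% reproduces. Progression times do not enter this calculation. No figure is stated for PFS.

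**3. Direction and size of a possible PFS bias (illustration)**

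Assumptions:

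- PFS on treatment is exponential with median 11 months. The figure is borrowed from the idelalisib FL value in the study rationale (Section 2), so λ = ln 2 / 11 = 0.0630 per month.
- A share q of patients is assigned a stop time uniform over 0 to 5.5 months (about six 28-day cycles).
- After stopping, the progression hazard is hλ.
- The analysis censors at the stop.

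The documents supply neither q nor h.

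Censoring at the stop leaves only on-treatment hazard in the Kaplan-Meier estimate, so its median stays at 11.0 months whatever q and h are. For t > 5.5 the true curve is

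S(t) = (1 − q)·e^(−λt) + q·e^(−hλt)·c, with c = [e^((h−1)·5.5λ) − 1] / [(h−1)·5.5λ], and c = 1 when h = 1.

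Setting S(t) = 0.5 gives the true median in months:

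| h | q = 10% | q = 20% | q = 30% | Bias of the censored estimate |
|---|---|---|---|---|
| 0.5 | 11.5 | 12.0 | 12.7 | downward |
| 1 | 11.0 | 11.0 | 11.0 | none |
| 1.5 | 10.7 | 10.3 | 10.0 | upward |
| 2 | 10.4 | 9.8 | 9.3 | upward |
| 3 | 10.0 | 9.2 | 8.4 | upward |

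A simulation of 200,000 patients per cell agrees to within 0.1 month. At q = 20% the overstatement is 11.0 − 10.3 = 0.7 months for h = 1.5 and 11.0 − 9.8 = 1.2 months for h = 2.

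**4. Scale against sampling error**

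At 12 months with q = 20% and h = 2, the censored estimate is e^(−12λ) = 0.469. The true value is 0.8 × 0.469 + 0.2 × e^(−24λ) × 1.195 = 0.376 + 0.053 = 0.428, a shift of about 4 percentage points. With 20 patients fully followed, the binomial standard error is √(0.43 × 0.57 / 20) = 0.11, or 11 points.

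**The case against.** A reader might infer that everyone who stops before completing six cycles is followed for toxicity alone. The documents do not support that. Section 6 orders progression follow-up after a delay over four weeks, and such a delay is the only discontinuation trigger named in the dose-hold table. Sections 10 and 11 set a CT schedule with no stable-disease condition, the calendar's CT row appears to carry a mark in a post-treatment column, and Section 5 asks for final-visit procedures at discontinuation. This part of the objection stands and confines the gap to stops for other reasons. It does not close the gap. The first two scan times are defined by cycles that an early stopper may not reach, nothing says that the later scans apply to such a patient, and Section 6 contradicts itself.

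A reader might also infer that PFS is biased upward. That does not follow either. No censoring rule is written, and the sign depends on what happens to the hazard after stopping. A rise is plausible when an active drug is withdrawn, but the documents do not show it.

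Nor does the phase I report that 19 of 24 patients remained on therapy establish a 20% early-stop rate. The study enrolled mixed histologies, the reasons for stopping are not given, and time on study ran from 3 to 49+ weeks. Patients who stopped for progression would be PFS events, not early censorings.

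Finally, PFS is descriptive here and the illustrated shift is well inside sampling error. That limits the priority of the point. It does not justify leaving avoidable missing data, because bias from informative censoring adds to sampling error and is not shown by a confidence interval.

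**Conclusion.** The concern holds as a gap and an inconsistency. For patients who stop before completing six cycles without progression and without a delay over four weeks, no section expressly requires follow-up for progression. For those with such a delay, Section 6 gives two incompatible instructions. Scan intervals differ between Section 5 and Sections 10 and 11.

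The effect on PFS and DoR is a risk of bias of unknown sign. The range of 0.7 to 1.2 months upward rests on an 11-month exponential median, 20% assigned an early stop, 1.5 to 2 times the hazard afterwards, and censoring at the stop. None of these is a finding about this trial. The same calculation gives no bias with an unchanged hazard and about 1 month downward with half the hazard. DoR was not modelled, but it is exposed to the same mechanism. The primary ORR test and its 87% power are unaffected. The change should be made because it is cheap and the missing dates cannot be recovered later; it does not threaten the main result.

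**What to change.** 1. Keep the existing CT sentence in Section 5, so that nothing is lost for patients who continue, and add:

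> All treated patients who stop study drug without progression, whatever the number of cycles received and the reason, remain in follow-up for progression. Progression status and results of standard-of-care imaging are collected at the three-monthly visits, and by record review or contact after one year, until progression, death, new anti-lymphoma therapy or withdrawal of consent.

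2. Reconcile Sections 5, 6, 10 and 11 on removal from the study versus continued follow-up, and on the scan interval. The study team must settle which rule applies.

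3. In Section 13, state the PFS and DoR events, the censoring rules (including new therapy and early discontinuation) and the estimator. Add a sensitivity analysis that counts early discontinuation without progression as an event, labelled as a conservative bound because it pushes PFS downward.

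The cost is an amendment to wording and a little more data capture for a few patients. The added sentence requires no extra scan. Part of the follow-up falls after the scheduled year, so existing visits do not cover all of it.

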6. DOSING DELAYS/DOSE MODIFICATIONS

- For a new treatment cycle to begin, patients must meet the criteria outlined in section 5. Moreover, all other toxicity must have returned to grade ≤ 2 . If either of these conditions are not met, the study drug will be held.
- If interruption of study drug lasts for more than 28 days, treatment should be discontinued and the subject should be removed from the study (please contact the study chair to discuss longer interruptions).
- Patients who experience toxicity and require the study drug to be withheld may not be candidates for biopsy. Patients who miss 4 or more doses of drug prior to a planned biopsy should be considered ineligible for biopsy. The treating physician will make the ultimate decision in this regard.

Dose Modifications

Patients will be monitored continuously for toxicity while on study therapy. Toxicity will be assessed using the NCI CTCAE v4.0 (<http://evs.nci.nih.gov/ftp1/CTCAE/CTCAE>) grading scale. If a patient has an adverse event of particular severity or had an adverse event at least possibly related to study drug, then dose modifications will be made according to the guidelines.

Deviations from these guidelines may occur only if agreed upon by the Principal Investigator. There should be no attempt to make up for doses omitted due to toxicity.

A maximum four (4) week delay of treatment for recovery from toxicity is allowed to recover from hematologic toxicities to \leq Grade 3 or non-hematologic toxicities to \leq Grade 2 or to baseline level. If greater than a four (4) week delay is necessary, then the patient should discontinue treatment

and continue to be followed for progression. If a patient withdraws consent or has documented progression, an end of study visit should be completed.

Recommended treatment interruptions/holds or dose modifications are summarized below and may be based on the clinical judgment of the Investigator with notification to the Principal Investigator. For an individual patient, dose reductions and discontinuations may be more conservative than indicated. (i.e., to dose-reduce or discontinue for non-hematologic toxicity of lower grades) based on the clinical judgment of the Investigator with notification to the Medical Monitor/Sponsor.

Summary of Dose Holds for Treatment-Related Toxicities

NCI-CTCAE Grade	Dose Delay and/or Modification
Hematologic Adverse Event	
Neutropenia	
Grade ≤ 2 neutropenia	Maintain current dose. Consider supportive care as warranted.
Grade 3 neutropenia	Maintain current dose, consider supportive care. If recurrence or persistent Grade 3, the next lower dose level will be allowed.
Grade 4 neutropenia or occurrence of neutropenic fever or infection	Delay TGR-1202 until Grade ≤ 3 and/or neutropenic fever or infection is resolved; thereafter, resume at full dose. Consider supportive care. If delay is > 4 weeks discontinue study drug. If recurrence after rechallenge, resume at the next lower dose level at discretion of the investigator.
Thrombocytopenia	
Grade ≤ 3 thrombocytopenia	Maintain current dose level and provide supportive care as clinically warranted.
Grade 4 thrombocytopenia	Delay TGR-1202 until Grade ≤ 3 ; thereafter, resume at full dose. Consider supportive care intervention as warranted. If delay is > 4 weeks, discontinue TGR-1202. If recurrence after rechallenge, resume at the next lower dose level.
Pulmonary & Related Infections*	
Grade ≥ 2	Withhold TGR-1202 as warranted, provide supportive care. Resume at full dose. If recurrence after rechallenge, resume at the next lower dose level.
*While pneumonitis has been minimal with TGR-1202, it is a reported adverse event associated with other PI3K delta inhibitors. PCP and anti-viral prophylaxis is required for any study patient.	
All Other Non-Hematological Adverse Events	
Grade ≤ 2	Maintain current dose level

Grade ≥ 3	Withhold TGR-1202 until Grade ≤ 2 . Resume at full dose. If recurrence after rechallenge, resume at the next lower dose level.
----------------	--

Study Drug Dose Levels

Study Drug	Starting Dose	1 st Dose Reduction	2 nd Dose Reduction
TGR-1202	800 mg	600 mg	400 mg

If a patient requires a dose reduction of TGR-1202 due to study drug related toxicity, the dose may not be re-escalated. If further evaluation of the toxicity reveals the event was not related to TGR-1202, this must be recorded in the medical record and dose re-escalation to the next higher dose level may be considered at the discretion of the investigator.

Ordering TGR-1202

Once the clinical study site receives regulatory approval (IRB/IEB), and the Sponsor and/or Sponsor designee performs the Site Initiation Visit and inspection of pharmacy, and determines the site to be officially open for enrollment, and once a patient is identified, a shipment of predetermined quantity of TGR-1202 will be shipped to the clinical study site.

Upon receipt of drug supplies, the Pharmacist or the designee from the site should update the accountability forms for TGR-1202. If any abnormality on the supplied bottles (TGR-1202) is observed, the Pharmacist or the appropriate person must document that on the acknowledgement of receipt and contact that Sponsor and/or Sponsor designee.

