 - c. Symptomatic or documented congestive heart failure that meets New York Heart Association (NYHA) Class III to IV definitions (see Appendix 6);
 - d. History of stroke within the last 6 months prior to screening

Inclusion of Women and Minorities

Both men and women of all races and ethnic groups are eligible for this trial.

Treatment Plan

Patients will be treated with TGR-1202 at a dose of 800 mg daily from day 1 to 28 on a 28-day cycle.

Duration of Treatment

Patients will be treated until one of the following events occurs:

- Disease progression
- Unacceptable adverse event(s)
- Withdrawal of consent
- Changes in the patient's condition that render continuation of the study drug unacceptable in the judgment of the treating physician
- An event that in the judgment of the treating physician warrants discontinuation of therapy.
- Patient withheld study drug for >28 days

Sample Size

The study will accrue a total of up to approximately **20 patients**.

Safety

Patients will be monitored carefully for the development of AE. AE will be evaluated according to criteria outlined in the National Cancer Institute (NCI) Common Terminology Criteria for Adverse Events (CTCAE), version 4.0.

Efficacy Outcome

Patients will be monitored for clinical and/or radiographic evidence of disease response. Response will be evaluated using clinical parameters, CT or PET/CT scan (PET/CT scan is preferred), and bone marrow or other tissue biopsy, according to the *Updated Recommendations for Evaluation, Staging, and Response Assessment for Hodgkin and Non-Hodgkin Lymphoma: The Lugano Classification.* (Cheson et al., 2014b)

Figure 1: Study Plan Flow Chart

[figure not shown]

Figure 2. Pharmacokinetics (PK) schedule

Pharmacokinetic studies

Cycle 1, days 1 and 15; cycle 2 , day 15; cycle 4, day 15

[figure not shown]
[figure not shown]

Figure 3. Pharmacodynamic (PD) Schedule

Pharmacodynamic studies on peripheral blood*

Cycle 1, days 1 and 15; cycle 2, day 15; cycle 4, day 15

Pharmacodynamic studies on tumor cells, blood cells, and buccal fibroblasts*

Screening, Cycle 2, day 15 (mandatory); cycle 4, day 15 (optional); end of treatment/POD (optional)

[figure not shown]
[figure not shown]

Figure 4. Study schema

¹ Includes tumor cells, blood cells, and buccal fibroblasts; tumor tissue includes nodal or extranodal tumor tissue that can be visualized and/or palpated + bone marrow aspiration and biopsy if bone marrow positive for lymphoma; ²

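### For a toxicity hold beyond 28 days, Section 6 both removes the patient from the study and keeps the patient in progression follow-up; the two sentences must be reconciled to protect PFS and DoR data

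*Combined protocol and SAP*

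**What the plan says.** Two current instructions in Section 6 apply to a long interruption.

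- Opening bullets: "If interruption of study drug lasts for more than 28 days", then "treatment should be discontinued and the subject should be removed from the study". A parenthesis adds "please contact the study chair to discuss longer interruptions". No cause of interruption is specified.
- Dose Modifications, on recovery from toxicity: "If greater than a four (4) week delay is necessary, then the patient should discontinue treatment" "and continue to be followed for progression".

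Other places touch the same event without settling it.

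- The synopsis (Duration of Treatment) lists "Patient withheld study drug for >28 days" among the events that end treatment. It does not mention study removal or follow-up.
- The dose-hold table in Section 6 says, for grade 4 neutropenia, "If delay is > 4 weeks discontinue study drug", with a similar line for thrombocytopenia. It too is silent on follow-up.
- Section 5, Criteria for Removal from Study, states "Patients will be removed from treatment when any of the criteria listed in Section 5.3 applies". The heading speaks of the study and the sentence of treatment.
- Section 5, Duration of Follow Up, has three-monthly visits for a year or until new treatment, for the purpose of delayed toxicity. Tumor assessment until progression is written only for patients who are at least stable once six cycles are done.

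PFS and DoR are secondary objectives, to be described (Section 1). Section 13 gives an exact confidence interval for ORR, but no definition, estimator or censoring rule for PFS or DoR.

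**The concern.** A patient cannot leave the study and also remain in it for progression follow-up. Four weeks is 28 days, so every toxicity hold past that limit triggers both sentences.

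If the off-study sentence is followed, scans stop before progression. PFS and DoR then have no event for that patient. Any later response is also missed, although best response (Section 11) is meant to run from the start of treatment until progression. Data not collected cannot be recovered at analysis. With 20 patients, each one lost is 5% of the sample, and the coordinating and participating centers could follow different sentences.

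If patients with long holds have a different risk of progression from the rest, ending their follow-up at the hold biases a time-to-event summary.

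**Working it through.** **The plan's own figure.** Section 13 gives 20 patients, null ORR 0.33, alternative 0.60, one-sided alpha 0.10 and power 87%. With an exact binomial test that rejects at 10 or more responses, alpha = P(X ≥ 10 | 20, 0.33) = 0.0866 and power = P(X ≥ 10 | 20, 0.60) = 0.8725. A cut-off of 9 gives alpha 0.182, which is too large. The 87% is reproduced and does not depend on the hold rule.

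**The two rules side by side.**

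| | Opening bullets | Dose Modifications |
|---|---|---|
| Trigger | more than 28 days, any cause | more than 4 weeks, toxicity |
| Treatment | stops | stops |
| Study follow-up | ends | continues for progression |

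The direct conflict is for toxicity holds. For other interruptions only the off-study bullet applies.

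**Illustration of the effect on PFS.** The plan has no PFS assumption, so these inputs are assumptions:

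- PFS is exponential with median 11 months, the figure Section 2 gives for idelalisib in FL. So λ = ln 2 / 11 = 0.0630 per month.
- A fraction f has hazard hλ from the start of treatment, and those still progression-free are lost at the end of cycle 2, c = 56 / 30.4375 = 1.84 months.
- The analysis is Kaplan-Meier, censoring at loss.

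True survival is S(t) = (1 − f)e^(−λt) + f·e^(−hλt), and the true median solves S(t) = 0.5. After c only the remaining patients are seen, so the Kaplan-Meier curve is S(c)·e^(−λ(t − c)), with median c + ln(2S(c)) / λ.

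Worked case, f = 0.2 and h = 2. Put x = e^(−λt). Then 0.2x² + 0.8x − 0.5 = 0, so x = (−0.8 + √1.04) / 0.4 = 0.5495 and the true median is −ln(0.5495) / 0.0630 = 9.50 months. S(c) = 0.8 × 0.8905 + 0.2 × 0.7930 = 0.8710, so the Kaplan-Meier median is 1.84 + ln(1.742) / 0.0630 = 10.65 months.

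| f | h | True median | Kaplan-Meier median | Difference |
|---|---|---|---|---|
| 5% | 2 | 10.61 | 10.91 | +0.30 |
| 10% | 2 | 10.23 | 10.83 | +0.60 |
| 20% | 2 | 9.50 | 10.65 | +1.15 |
| 30% | 3 | 7.72 | 9.98 | +2.26 |
| 20% | 1 | 11.00 | 11.00 | 0 |
| 20% | 0.5 | 12.46 | 11.19 | −1.27 |

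**Later holds.** A simulation of 400,000 patients per scenario started holds at 2 to 8 months and raised the hazard only afterwards. With 10% of patients and hazard ratio 1.5, the median was 10.72 months if followed and 10.99 if censored. With 30% and hazard ratio 3, it was 9.05 and 11.00. The difference is again about 0.3 to 2 months, and about zero at hazard ratio 1.

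**The case against.** The best defense is that the off-study wording is loose. Section 5 places removal from treatment under a heading about removal from study, follows patients removed for unacceptable adverse events until those resolve or stabilize, and schedules three-monthly visits after the end-of-study visit. The Dose Modifications sentence is the more specific one for toxicity, and the text after it links the end-of-study visit to withdrawn consent or documented progression. The reading is plausible, but the text does not state it, and it concedes that the wording needs correcting. None of those provisions orders scans after a hold. The Study Calendar carries a late CT mark whose column is hard to place in the extracted table; its footnote ties scans to cycles 2 and 6 and later restaging, and does not say that patients off drug stay on that schedule.

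A reader might infer that PFS and DoR will be informatively censored and so overstated. The documents do not support that. They give no PFS or DoR estimator or censoring rule, no rate of holds beyond 28 days, and nothing on prognosis after such a hold. The off-study bullet covers any interruption, so patients held this long need not be those with persistent toxicity. The largest scenarios are also demanding: to pass 28 days of hold by the end of cycle 2, a patient must have stopped drug in cycle 1. Section 2 reports no grade 3 or higher event in 10% or more of phase I patients, and 19 of 24 patients starting at 800 or 1200 mg of the micronized formulation still on therapy. That leaves 5/24 = 21% off for any reason.

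Scale matters too. With 20 patients, complete follow-up and a true median of 11 months, the sample median has a standard deviation of about 3.5 months, so a shift of 1.15 months is about a third of the sampling noise.

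These points limit the consequence. They do not remove the contradiction.

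**Conclusion.** The contradiction stands. For toxicity holds beyond 28 days, Section 6 orders both removal from the study and continued follow-up for progression, and no other text resolves it. Following the first would leave progressions and responses uncollected, most clearly for patients who stop before completing six cycles.

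Bias in PFS and DoR is a possibility, conditional on long holds being related to prognosis. Under the stated assumptions, the error in the PFS median runs from about 1.3 months too low to about 2.3 months too high, and is zero if there is no relation. The lost fractions, the hazard ratios, the exponential shape and the use of Kaplan-Meier are all assumptions. No figure was worked out for DoR.

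The endpoints affected are descriptive and secondary. The 87% power for ORR stands. A late response in a removed patient could go unrecorded, but the documents give no basis for sizing that. The change should be made, because lost follow-up cannot be repaired later; it does not threaten the primary design.

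**What to change.** - Reconcile the two Section 6 sentences so that off treatment and off study are distinct states. This leaves every treatment-stopping rule as it is and takes no view on the hold limit.
- State that patients who stop drug without progression, for whatever reason, stay in study follow-up for response, PFS and DoR until progression, death or withdrawal of consent. Align Criteria for Removal from Study and Duration of Follow Up in Section 5, so that tumor assessment is not confined to patients who complete six cycles.
- Section 13 states no censoring rule for PFS or DoR, so say there how the start of new lymphoma treatment before progression is handled.

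The cost is a wording amendment, plus tumor assessments for the few patients concerned. For toxicity holds, the Dose Modifications sentence already calls for that follow-up.
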